The evaluation of the Parent Navigation NICU to home program will use a randomized trial design. We will do so by recruiting a population of parents who have an infant in the Children's National NICU, half of whom will receive enhanced usual care by provision of a NICU care notebook and half of whom will receive the same enhanced care- including care notebook- plus Parent Navigation (intervention). All will be patients in the NICU who are discharged from the CNMC NICU. Group assignment will be by randomization, stratified by birth weight (≤ 1500 grams or >1500 grams). The design incorporates extensive measurement of baseline attributes to assess the comparability of intervention and enhanced control groups at inception.

We aim to enroll $n=300$ parents of infants receiving care in the Children's National NICU who are discharged from the CNMC NICU. CNMC has a Level IV NICU which receives a large number of complex cases. To allow for generalization of study findings to other NICUs and other centers, we will enroll all patients discharged from the CNMC NICU.

Study personnel will identify eligible NICU patients by reviewing NICU census data or through the use of the PowerTrials Prescreening function. PowerTrials is a HIPAA-compliant application that is integrated into the Children's National Cerner electronic medical records system (PowerChart). Study inclusion and exclusion criteria will be used to create a Prescreening Rule. A screening engine in PowerChart will compare the criteria to patient data within the medical records system, and a list of potential study subjects will be generated.

Research study staff will approach parents anticipating discharge within 1-2 weeks to invite their participation and, as appropriate, obtain informed consent. If parents of eligible patients are not available, we may contact a parent by phone to set up a time to discuss the study in person. We will obtain in person signatures of consent as appropriate before enrolling potential participants in the study. Recruitment will continue in this fashion until the required sample is enrolled.

Inclusion criteria include:

NICU patients discharged from the CNMC NICU. One parent participant per NICU patient will be identified and enrolled as the participant.

Exclusion criteria include:

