**GPS (Giving Parents Support): Parent Navigation After NICU Discharge**

**NCT02743472**

**Statistical Analysis Plan**

**Updated/approved by Children's National IRB: 2/15/17**

**PI: [name], MPH**

### **Statistical Considerations:**

We will conduct intent-to-treat analyses to assess effects of the PN intervention such that randomized families will be analyzed according to their assigned intervention group, regardless of departures from the randomized intervention. While it is possible that families may seek some type of parental support independently of the intervention, these potential effects may be evaluated in sensitivity analyses. Our analysis strategy will first compare baseline characteristics between the PN and control groups to evaluate the balance produced by randomization. It is expected that randomization with stratification on one key confounder of birth weight ( $\leq 1500$  grams or  $>1500$  grams) will result in a balanced distribution of factors between the PN and care resource groups on most, if not all factors. However, even with randomization some imbalance may occur on a few factors and it is important to identify such factors, as these are the ones that need to be controlled during analysis.

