Aim 1a. and 1b. The outcome measures involved in this aim (e.g., parenting self-efficacy measured using the PMP S-E and perceived stress scale), are derived from multi-item scales and will be treated as continuous measurements. For each scale, the mean score after baseline will be assessed at each of the visits (1 week, 1 month, 3 months, 6 months and 12 months). The overall mean difference from baseline for each of the scales between the two intervention groups will be used to evaluate Aim 1. We will assess the overall change in scores for the self-efficacy and depression scales, i.e. the population averaged effect of the intervention on changes in self-efficacy and depression, using a generalized estimating equation (GEE) model to account for the correlation between the repeated change measurements among primary care givers. The GEE model is reasonably robust to missing data. We will use an exchangeable correlation structure, but in sensitivity analyses, will also test unstructured correlation and compare parameter estimates. The main independent variable in these analyses is intervention group, however we will also include (if necessary) a cross-product term of group-by-time which will enable us to estimate differences between the intervention groups over time. The group-by-time term will be included only if it is statistically significant. The model will include covariates reflecting the randomization stratification variables, and other covariates only if imbalances are observed in the randomization groups at baseline. In addition, we will use the model to plot the change in parental self-efficacy or parenting stress over time-by-group with 95% CI around each time point estimate. The degree of change at 3-months will allow us to assess the rapidity of any effect of intervention and a descriptive comparison of the differences between the groups at 6- and 12-months will allow us to assess the degree of persistence of any effect. We will consider the difference between groups to be statistically significant when the 95% confidence intervals around the difference do not include 0.

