Aim 2a. and 2.b. will compare measures of anxiety using the STAI, and depression using the CES-D in primary caregivers from the intervention and control groups. The independent variable will be the intervention group in both models. If necessary, the models will include covariates known to impact parental depression and anxiety (if different between the groups) and stratification variables. We will estimate and compare the covariate adjusted mean difference in the scores between the intervention

groups using GEE models as described above (Aim 1). The difference will be considered to be statistically significant if the 95% CI around the difference fails to include 0.

As in Aim 1, group-by time-interaction models will be used to evaluate differences between the groups over time.

Aim 3. The NICU graduates may experience multiple ED visits or hospitalizations any time after baseline. The number of ED or hospitalization counts will be summed for each of the intervention groups. To assess differences between the intervention groups for each of the outcomes (ED visits or hospitalizations), we will use the Wilcoxon–Mann–Whitney two-sample rank-sum test, which is appropriate for use with nonparametric data, such as the count data from this aim. We will define the outcome, improved immunization status, as receipt of two diphtheria-tetanus-acellular pertussis (DTaP) vaccines, two Hemophilus influenzae b (HIB) vaccines, and two pneumococcal conjugate vaccines (PCV-13) by the end of the observation period (12 months after baseline). This binary outcome will be contrasted using an unpaired t-test with unequal variances to measure the hypothesis that the intervention results in improved immunization status.

Sensitivity Analyses. In sensitivity analyses, we will explore the effect of departures from assumptions made for the main analysis. A key assumption in our analyses is that missing data are missing at random, and groups who are and are not lost to follow-up are similar. We will compare characteristics of families who are, and are not, lost to follow-up. If significant differences between these two ( $p < 0.05$ ) are observed, we can test for intervention effects, but with the assumption that individuals with missing data have worse outcomes. We will then report these ‘worst case’ scenarios and report any changes in the clinical interpretation of the trial.

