Sample Size & Power. We calculated power to detect projected differences between the intervention groups for the 3 primary outcomes. All computations are based on a projected sample size of 300 families of NICU infants (i.e. 300 primary care giver evaluations, and 300 NICU infant outcome evaluations) with randomization into 2 equal groups of 150, with data collected over multiple time points during the 12 months of follow-up post discharge. In Aims 1 and 2, we will have up to 5 repeated measures after baseline (1-week, 1-month, 3-months, 6-months, and 12-months), which increases our statistical power for those aims. We assumed a modest within-subject correlation of 0.50 between these repeated measures. Using Bonferroni correction, we adjusted alpha (0.05) for the number of primary outcomes,  $n=3$ . For Aim 1, we estimate that we will have excellent power (93%) to detect differences in parental self-efficacy scores as small as 0.33SD. This estimate is based on PMSPE score distributions as reported in the literature. For the main infant outcome of number of hospitalizations during the 12-month follow-up post discharge period, we estimate that we have excellent power (99%) to detect a difference of 1 in the median number of hospitalizations between the groups. Given our conservative assumptions, including modest correlation ( $r=0.5$ ) between repeated measures and Bonferroni correction for the number of primary outcomes, we believe that our sample size ensures sufficient power to measure clinically relevant differences between the intervention groups.

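### The immunization comparison (Hypothesis 3c) leaves out the birth-weight stratum used at randomization: a minor loss of power that a stratified test avoids at no cost

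*SAP*

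**What the plan says.** The protocol (Research Design and Methods) states: "Group assignment will be by randomization, stratified by birth weight", with the cut at 1500 g. The SAP (Statistical Considerations, opening paragraph) refers to "randomization with stratification on one key confounder of birth weight".

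The aims then treat this factor in three ways:

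- **Aim 1 (GEE):** "The model will include covariates reflecting the randomization stratification variables".
- **Aim 2 (GEE):** "If necessary, the models will include covariates known to impact parental depression and anxiety (if different between the groups) and stratification variables".
- **Aim 3, immunization:** "This binary outcome will be contrasted using an unpaired t-test with unequal variances". No stratum or covariate is mentioned. The protocol's Aim 3 text is the same.

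The opening paragraph also says that factors found imbalanced at baseline should be controlled. Stratified randomization makes birth weight one of the factors least likely to be caught by that rule, and a two-sample t-test could not carry it anyway. The sensitivity analyses concern missing data and outside support, not stratification.

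**The concern.** When a trial randomizes within strata of a factor related to the outcome, the analysis should normally use those strata. If it does not, variation between strata stays in the error term and the comparison is less precise than the design allows. If the arms are also balanced within strata, the unstratified standard error overstates the true variability of the arm difference, so the test rejects less often than its nominal level.

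At stake is some power for Hypothesis 3c. The sample-size section gives power for self-efficacy and for hospitalizations, but none for immunization, so there is no stated margin to absorb a loss. The SAP gives no reason for using the factor in Aim 1 and omitting it here.

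**Working it through.** The plan states no power, coverage rate or effect size for immunization, so there is no planned figure to reproduce. The check asks what the missing stratum term costs under stated assumptions.

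**Inputs from the documents.** 300 families, "randomization into 2 equal groups of 150"; two birth-weight strata; a binary outcome.

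**Assumptions (not in the documents).** 35% of infants at or below 1500 g; control coverage by stratum as listed; a common odds ratio of 2.5; two-sided alpha of 0.05. The SAP says "Using Bonferroni correction, we adjusted alpha (0.05) for the number of primary outcomes", but gives no alpha for immunization and no sidedness.

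**Step 1. Is the t-test itself the problem?** No. At 150 per arm, the Welch t-test and the unstratified Pearson chi-square gave identical rejection rates in every simulated scenario where both were run.

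**Step 2. Approximate size when arms are balanced within strata.** Let f be the share at or below 1500 g, p1 and p2 the coverage in the two strata, and p = f·p1 + (1−f)·p2.

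- Within-stratum variance: W = f·p1(1−p1) + (1−f)·p2(1−p2)
- Total variance: T = p(1−p)
- R = W/T
- True size ≈ 2·[1 − Φ(1.96/√R)]

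For 60%/90% coverage:

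- p = 0.35×0.60 + 0.65×0.90 = 0.795
- W = 0.35×0.24 + 0.65×0.09 = 0.1425
- T = 0.795×0.205 = 0.1630
- R = 0.874, so 1.96/√R = 2.096 and size ≈ 3.6%

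The same steps give R = 0.968 and about 4.6% at 70%/85%, and R = 0.800 and about 2.9% at 50%/90%. With equal coverage R = 1 and the size is 5.0%.

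**Step 3. Simulation.** Welch t-test against the Cochran-Mantel-Haenszel (CMH) test without continuity correction; 200,000 trials per scenario; arms balanced within strata. An odds ratio of 2.5 turns coverage p into 2.5p/(1−p+2.5p); for example, 50% becomes 1.25/1.75 = 71% and 90% becomes 2.25/2.35 = 96%.

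| Control coverage, ≤1500 g / >1500 g | Gap (points) | Size, Welch | Size, CMH | Power, Welch | Power, CMH |
|---|---|---|---|---|---|
| 80% / 80% | 0 | 5.0% | 5.0% | 77.5% | 77.6% |
| 75% / 85% | 10 | 4.9% | 5.0% | 73.7% | 74.2% |
| 70% / 85% | 15 | 4.7% | 5.0% | 76.2% | 77.1% |
| 60% / 90% | 30 | 3.6% | 5.0% | 71.8% | 75.4% |
| 50% / 90% | 40 | 2.9% | 5.0% | 73.3% | 78.7% |

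The simulated sizes agree with Step 2.

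**Step 4. Without balance inside strata.** With coin-flip assignment within each stratum, the Welch size was 5.0% in every scenario. The power loss remained: 71.0% vs 75.2% at 60%/90%, and 71.7% vs 78.8% at 50%/90%.

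**Step 5. Sensitivity to the stratum share (balanced arms).** With a 30% share, the power loss was 3.8 points at 60%/90% (68.9% vs 72.7%) and about 6 at 50%/90% (70.1% vs 76.0%). With a 50% share, it was 2.4 points (80.2% vs 82.7%, before rounding 80.23 and 82.65) and 4.0 points (82.2% vs 86.1%, before rounding 82.17 and 86.13).

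**The case against.** The strongest reply is that this hardly matters. The documents give no coverage by birth weight and no stratum share, so a loss of more than about one point rests on an assumed gap well above 15 points. Immunization is not the main infant outcome; the power section gives that place to hospitalizations. No stated power claim fails. All of this stands, and it keeps the point minor. It is also true that the rank-sum tests for hospitalizations and ED visits carry no stratum term. That widens the omission but does not excuse it here; those tests were not examined in this check.

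Four stronger readings are tempting, and the documents do not support them:

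- **That a t-test on a 0/1 outcome is invalid here.** At 150 per arm it decides as the unstratified chi-square does, and switching to that chi-square would leave the stratum out just the same.
- **That the type I error is out of control.** Any departure caused by the missing stratum is downward, so a positive result would not be undermined. Even this needs balance within strata. The protocol describes a stratified REDCap scheme but does not mention blocks.
- **That some 10 points of power are lost.** A flat 10-point gain on 50%/90% coverage gives about 62% vs 73%, but it puts the intervention arm's >1500 g stratum at exactly 100%, with no variance left. With a common odds ratio of 2.5 and the same control coverage, the loss is 5 to 7 points.
- **That a t interval could run past 100%.** The planned contrast is a difference between arms, which lies near zero when coverage is very high in both. No per-arm t interval is planned.

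**Conclusion.** The point holds as a minor matter of efficiency. The immunization test omits a factor that the plan randomizes on, calls a key confounder and uses in its Aim 1 model. If coverage differs by birth weight, the omission costs power on the scale shown in the table. If coverage is the same in both strata, it costs nothing.

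The direction does not depend on the assumed inputs; the size does. It rests on the assumed stratum share, coverage rates, odds ratio and two-sided 0.05 level. The conservatism further requires arms balanced within strata. This is not a threat to validity, and it does not bear on the outcomes for which the plan states power.

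**What to change.** In Aim 3 of the SAP, and in the matching protocol text, replace the t-test sentence with a Cochran-Mantel-Haenszel test and a Mantel-Haenszel risk difference with 95% CI, both stratified by birth weight (≤1500 g / >1500 g). State the alpha and sidedness in the same sentence.

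A logistic model with arm and stratum, reporting a standardized risk difference, would also serve. It is less robust if coverage in a stratum approaches 100%, because the fit can then fail through separation.

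The cost is one sentence in each document. The stratum is already recorded at randomization, so no new data are needed. In the equal-coverage scenarios run here, the stratified test lost at most about 0.2 point of power. The change brings the immunization analysis into line with Aim 1 and gives readers an estimate on the risk scale.

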Aim 2a. and 2.b. will compare measures of anxiety using the STAI, and depression using the CES-D in primary caregivers from the intervention and control groups. The independent variable will be the intervention group in both models. If necessary, the models will include covariates known to impact parental depression and anxiety (if different between the groups) and stratification variables. We will estimate and compare the covariate adjusted mean difference in the scores between the intervention groups using GEE models as described above (Aim 1). The difference will be considered to be statistically significant if the 95% CI around the difference fails to include 0.

As in Aim 1, group-by time-interaction models will be used to evaluate differences between the groups over time.

Aim 3. The NICU graduates may experience multiple ED visits or hospitalizations any time after baseline. The number of ED or hospitalization counts will be summed for each of the intervention groups. To assess differences between the intervention groups for each of the outcomes (ED visits or hospitalizations), we will use the Wilcoxon–Mann–Whitney two-sample rank-sum test, which is appropriate for use with nonparametric data, such as the count data from this aim. We will define the outcome, improved immunization status, as receipt of two diphtheria-tetanus-acellular pertussis (DTaP) vaccines, two Hemophilus influenzae b (HIB) vaccines, and two pneumococcal conjugate vaccines (PCV-13) by the end of the observation period (12 months after baseline). This binary outcome will be contrasted using an unpaired t-test with unequal variances to measure the hypothesis that the intervention results in improved immunization status.

Sensitivity Analyses. In sensitivity analyses, we will explore the effect of departures from assumptions made for the main analysis. A key assumption in our analyses is that missing data are missing at random, and groups who are and are not lost to follow-up are similar. We will compare characteristics of families who are, and are not, lost to follow-up. If significant differences between these two ($p < 0.05$) are observed, we can test for intervention effects, but with the assumption that individuals with missing data have worse outcomes. We will then report these ‘worst case’ scenarios and report any changes in the clinical interpretation of the trial.

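### The only missing-outcome sensitivity analysis is optional, hangs on a test that cannot see unobserved scores, and as plainly read is not a worst case for a Parent Navigation benefit

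*SAP*

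**What the plan says.** The relevant text is the Sensitivity Analyses paragraph under Statistical Considerations, worded the same in the Protocol and the SAP.

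- Assumption: "A key assumption in our analyses is that missing data are missing at random". The same sentence adds that lost and retained families are taken to be similar.
- Check: "We will compare characteristics of families who are, and are not, lost to follow-up". The characteristics are not listed, and no comparison of loss between arms is planned.
- Trigger: "If significant differences between these two" groups are seen at p<0.05, the team may proceed.
- Analysis: "we can test for intervention effects, but with the assumption that individuals with missing data have worse outcomes". No penalty size is given and the arms are not mentioned.
- Use: "We will then report these ‘worst case’ scenarios and report any changes in the clinical interpretation of the trial".

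For the main analysis, the Aim 1 paragraph says "The GEE model is reasonably robust to missing data" and describes no imputation or weighting. The power paragraph assumes "randomization into 2 equal groups of 150" with all 300 families evaluated. Neither document gives an expected dropout rate, overall or by arm.

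**The concern.** A missing-data sensitivity analysis should ask how far the conclusion depends on outcomes nobody saw. Here it is reached only through a significance test on things that were seen. A non-significant result does not show that missingness is ignorable, and no alternative missing-outcome analysis is described for that case. The unstructured-correlation analysis is not gated, but it does not address missing outcomes.

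The scenario itself is the second difficulty. To challenge a claimed PN benefit, the missing PN families must be made worse relative to the missing control families. Making everyone with missing data worse does this only if PN loses more families. With equal loss the penalty cancels from the difference, and with more loss in control it moves the result towards PN. The reader would then see a claimed benefit survive, or grow, under an analysis called 'worst case'. Loss by arm decides the direction, and the plan does not examine it.

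**Working it through.** **The plan's own figure.** This paragraph states no number except p<0.05. The nearest figure is the 93% power for 0.33 SD in self-efficacy. With 150 per arm, five post-baseline visits and r = 0.5, the variance of a family's mean score is (1 + 4 × 0.5)/5 = 0.6 in units of the single-visit variance, so SE = √(2 × 0.6/150) = 0.0894 SD. Power is 90.2% at two-sided alpha 0.05/3 and 94.1% at one-sided 0.05/3. The documents do not state sidedness, so 93% is approached but not matched exactly. Nothing below depends on it; only the sample size, number of visits and correlation are carried forward.

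**Step 1: the trigger.** For one characteristic differing by d SD between lost and retained families, the chance of p<0.05 is Φ(d/√(1/n_lost + 1/n_retained) − 1.96). Take d = 0.3 (assumed).

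- 20% lost (60 vs 240): 0.3/0.1443 = 2.08, power 55%.
- 10% lost (30 vs 270): 0.3/0.1925 = 1.56, power 34%.
- Ten independent characteristics, none truly different: 1 − 0.95^10 = 40% chance of firing.

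So whether the analysis runs depends on how many families are lost and how many characteristics are tested. Neither says anything about the unobserved scores.

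**Step 2: the penalty, no true effect.** Assumptions: lost families miss all five visits; before the penalty, lost and retained families have the same mean in both arms; higher scores are better; missing families are lowered by k single-visit SDs in both arms. With p the share lost:

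- shift in PN − control = k × (p_control − p_PN)
- variance per arm = 0.6 + k² × p(1 − p), because the penalty adds spread
- chance of a significant PN benefit = Φ(shift/SE − 1.96), using the SAP's 95% CI rule

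Worked case, 10% PN and 30% control, k = 1: shift = 0.20; SE = √((0.6 + 0.09 + 0.6 + 0.21)/150) = √(1.5/150) = 0.100; Φ(2.00 − 1.96) = 52%.

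| Loss PN / control | Shift, k = 0.5 | False PN benefit | Shift, k = 1 | False PN benefit |
|---|---|---|---|---|
| 20% / 20% | 0 | 2.5% | 0 | 2.5% |
| 15% / 25% | +0.05 SD | 8% | +0.10 SD | 17% |
| 10% / 30% | +0.10 SD | 19% | +0.20 SD | 52% |
| 25% / 15% | −0.05 SD | 0.6% | −0.10 SD | 0.2% |

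If lost families miss only the last two of the five visits, each shift falls to 2/5 of its value. For 10%/30% and k = 1 it becomes 0.08 SD, with SE = √((1.2 + 0.16 × 0.30)/150) = 0.091 and about a 14% chance of a false PN benefit.

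**Step 3: a true effect of 0.33 SD, k = 1.**

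- 20% lost in each arm, both penalised: 0.33 + 1 × (0.20 − 0.20) = 0.33 SD, significant 91% of the time.
- Same loss, only PN dropouts penalised: 0.33 − 0.20 = 0.13 SD, significant 28% of the time.
- 15% PN and 25% control lost, both penalised: 0.33 + 0.10 = 0.43 SD. Only PN penalised: 0.33 − 0.15 = 0.18 SD.

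**The case against.** **Unequal loss is not established.** The Protocol uses the same data-collection procedures in both arms, updates contact details (including a locator contact) at each time point, and pays for each one. Against that, control parents are told their assignment and only PN families have a navigator who contacts them after discharge (Protocol, Description of Intervention). Higher control loss is therefore plausible but not shown. A reader might infer that the analysis will favour PN; the documents support only that it can, if control loses more.

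**Equal treatment of the arms is not stated.** It is the natural reading of a rule about all individuals with missing data, but the SAP does not say so, and the plural 'scenarios' leaves room for arm-specific versions. None is specified. This point stands as a limit on the criticism: the scenario is under-specified and, read plainly, not a worst case. It is not an explicit rule to penalise both arms identically.

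**The trigger may fire often.** The 55% and 34% apply to one characteristic tested alone, and the Protocol plans extensive baseline measurement. With ten independent tests, one of them a true 0.3 SD difference and 20% lost, it fires 1 − 0.453 × 0.95^9 = 71% of the time. This weakens the low-power argument. It does not rescue the trigger, which still tests the wrong thing and whose behaviour depends on an unstated list of characteristics.

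**The size is easy to overstate.** Using SE = 0.0894 for the 10%/30%, 1 SD case gives 61%, but that leaves out the variance the penalty adds; 52% is the figure. That case is also an extreme, assumed imbalance. A reader might further infer that the plan will change its conclusion on this analysis; it undertakes only to report any changes in the clinical interpretation, and the GEE result remains the main analysis.

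**Conclusion.** The concern holds in two parts. The trigger part follows from the text alone: the only missing-outcome sensitivity analysis is optional and conditional on a comparison that cannot detect missingness depending on unobserved scores, so the plan can be followed exactly and the check never made. The scenario part rests on the plain reading of the penalty rule. With equal loss the rule leaves a PN benefit unchallenged (0.33 SD stays 0.33 SD, against 0.13 SD when a 1 SD penalty falls on PN dropouts only, 20% lost per arm). With more loss in control it moves the estimate towards PN by 0.05–0.10 SD at 15%/25% and 0.10–0.20 SD at 10%/30%, for penalties of 0.5–1 SD.

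Every loss rate and penalty here is an assumption, and families are taken to miss all five visits; shifts are smaller when only late visits are missed and reverse when PN loses more. The SAP should be amended on this point, but nothing here shows that the trial's result would be wrong.

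**What to change.** 1. Delete the p<0.05 trigger and change 'can' to 'will', so the analysis is always run. The comparison of lost and retained families can stay as description.
2. Report loss to follow-up by arm and by visit.
3. Replace the unspecified common penalty with arm-specific penalties over a stated range. Include a scenario that penalises missing PN families with control left at missing at random.
4. Report the penalty at which the conclusion changes, so readers can judge whether it is plausible.

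Multiple imputation under missing at random, followed by shifts to the imputed scores, is one suitable way to do this; other methods that meet points 1 to 4 would also serve. The same wording should go into the Protocol paragraph. The cost is SAP and Protocol text and modest extra analysis, with no new data.

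### Bonferroni is the only multiplicity method named for the three primary outcomes and never reaches the decision rules; Holm's procedure, written into both places, would control the same 5% familywise error with equal or better power

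*SAP*

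**What the plan says.** The Sample Size & Power paragraph (under Statistical Considerations in both documents) opens: "We calculated power to detect projected differences between the intervention groups for the 3 primary outcomes". It then gives the correction: "Using Bonferroni correction, we adjusted alpha (0.05) for the number of primary outcomes", the number being three. The same paragraph later counts this correction among its conservative assumptions.

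Only two of the three outcomes can be identified from the power text:
- Self-efficacy: "we estimate that we will have excellent power (93%) to detect differences in parental self-efficacy scores as small as 0.33SD".
- Hospitalizations: "we estimate that we have excellent power (99%) to detect a difference of 1 in the median number of hospitalizations between the groups".

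The third is neither named nor given a power figure.

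The analysis paragraphs do not repeat the correction. Aim 1 and Aim 2 each call a group difference significant when its 95% confidence interval excludes zero. Aim 3 names a rank-sum test for hospitalizations but no significance level. Holm's procedure is not mentioned in either document.

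**The concern.** With three primary outcomes, single-step Bonferroni holds each one to 0.05/3 = 0.0167, whatever the other two show. Holm's procedure uses the same p-values. It compares the smallest with 0.0167, the next with 0.025 and the largest with 0.05, and stops at the first failure. It rejects everything that Bonferroni rejects, sometimes more, and controls familywise error at 5% under any dependence between the tests.

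The difference is largest when the other primary outcomes are also positive, which is what this plan expects, since it claims 99% power for hospitalizations. Suppose self-efficacy then has a p-value between 0.0167 and 0.025. Bonferroni, if applied, would call it unproven. Holm would call it significant once hospitalizations had been rejected.

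The plan also leaves open which level the tests will use. Someone has to settle that before analysis, and that is the time to choose the better procedure.

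**Working it through.** **Inputs from the Sample Size & Power paragraph**
- Sample: "All computations are based on a projected sample size of 300 families of NICU infants", "with randomization into 2 equal groups of 150"; no allowance for loss to follow-up.
- Repeated measures: "we will have up to 5 repeated measures after baseline".
- Correlation: "We assumed a modest within-subject correlation of 0.50 between these repeated measures".
- Self-efficacy effect 0.33 SD with stated power 93%; hospitalizations stated power 99%.

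**Assumptions, because the documents give no figure**
- The third outcome's effect.
- The correlation between the three test statistics, taken as 0, 0.5 or 0.7.
- The hospitalization power of 99% is taken as stated. No distribution is given, so it cannot be recomputed.

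**Step 1. The stated 93%.** The variance of the mean of five exchangeable measures, in SD² units, is (1 + 4 × 0.5)/5 = 0.60. For change from baseline it is 0.60 + 1 − 2 × 0.5 = 0.60, the same.
- SE = √(2 × 0.60/150) = 0.0894; 0.33/0.0894 = 3.69.
- Two-sided 0.0167, critical value 2.394: power = Φ(3.69 − 2.394) = 90.2%.
- One-sided 0.0167: 94.1%. Two-sided 0.025: 92.6%.
- Two-sided 0.05, which is the written Aim 1 rule: Φ(3.69 − 1.960) = 95.8%.

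The two-sided reading falls 2.8 points short of 93%. Both 90.2% and 93% are carried forward as starting points.

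**Step 2. Bonferroni against Holm.** Trivariate normal test statistics were simulated, 2,000,000 draws per scenario. The hospitalization mean was set to 2.394 + 2.326 = 4.72 so that its Bonferroni power is 99%. In the first three rows the third outcome has the same power as self-efficacy.

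| Scenario | Self-efficacy power, from 90.2% | From stated 93% |
|---|---|---|
| All three real, correlation 0 | 95.6% (+5.3) | 97.1% (+4.0) |
| All three real, correlation 0.5 | 95.0% (+4.8) | 96.7% (+3.7) |
| All three real, correlation 0.7 | 94.7% (+4.5) | 96.4% (+3.4) |
| Third outcome null, correlation 0 | 92.7% (+2.5) | 94.9% (+1.9) |
| Only self-efficacy real, correlation 0 | 90.3% (+0.1) | 93.1% (+0.1) |

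Gains are in percentage points and were taken before rounding. The fourth row can be checked by hand: hospitalizations are nearly always rejected, so self-efficacy is in effect tested at 0.025, where step 1 gives 92.6%.

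**Step 3. Familywise error when all three nulls are true**
- Bonferroni, independent tests: 1 − (1 − 0.05/3)³ = 4.9%. Holm is the same, because any rejection needs the smallest p-value to be below 0.0167. At correlation 0.5 both are 4.4%.
- Uncorrected 0.05 for all three: 1 − 0.95³ = 14.3% if independent, and 12.6% at correlation 0.5.

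**The case against.** The strongest objection is that no power is lost to Bonferroni under the rules as written. A reader might infer from the power paragraph that the trial is already giving up about 5 points on self-efficacy. The documents do not support that. The correction is described only as something done in the power calculation, while Aim 1 decides by an ordinary 95% interval. Under that rule self-efficacy has 95.8% power, slightly more than Holm gives from the same 90.2% base. This stands, so the loss is conditional on applying the named correction. It does not remove the point: uncorrected tests of all three primaries would not hold the familywise 5% that the power paragraph planned for, so a rule has to be chosen.

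A second objection is that the size of the gain depends on assumptions. That also stands. The upper figures need all three effects to be real and an unnamed outcome to have self-efficacy's power. If the third outcome were depression, the CES-D is not given at 1 week (Protocol, Study Design and Data Collection). With four follow-up measures, power at 0.33 SD and 0.0167 would be 88.9%. Larger gains appear for the chance that all three outcomes are significant (7.8 to 10.8 points from the 90.2% base), but the plan does not set that as a goal.

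Third, Bonferroni is valid, leaves self-efficacy at about 90% with full retention, and gives simple simultaneous 98.33% intervals that match its decisions. Holm has no equally simple intervals, and this plan decides by intervals. This is a real cost of the change.

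**Conclusion.** The point holds as a conditional one. Bonferroni is the only multiplicity method named, and it stops at the power calculation. If it is applied to the tests, it costs self-efficacy between about 0.1 and 5.3 points of power compared with Holm, with no gain in familywise error control. The middle case, about 2.5 points (1.9 from the stated 93%), needs no assumed effect for the third outcome, but it does rely on the stated 99% for hospitalizations. If the uncorrected rule is used for all three instead, familywise error is about 13 to 14%. That figure assumes 0.05 for hospitalizations too, where the plan states no level.

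Two stronger readings should be avoided. Bonferroni is not an error, and the change recommended here is an improvement in efficiency. Nor is the stated 93% shown to be wrong: the power paragraph does not state sidedness, and a one-sided calculation gives 94.1%.

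**What to change.** Make these changes in both documents:

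1. Name the three primary outcomes, with one prespecified test and p-value for each. Holm's procedure cannot be run without this.
2. In Sample Size & Power, replace the Bonferroni sentence with a statement that the three primary outcomes are tested by Holm's step-down procedure at a two-sided familywise 0.05, with ordered p-values compared with 0.0167, 0.025 and 0.05. Keep the 0.0167 calculation as the lower bound for power, and add the Holm figure with its assumptions.
3. In the Aim 1, Aim 2 and Aim 3 paragraphs, state that conclusions on the primary outcomes are read from Holm-adjusted p-values. For those outcomes, remove the rule that a 95% interval excluding zero is sufficient. Changing the power paragraph alone would leave two conflicting rules.
4. If simultaneous intervals are wanted, report 98.33% intervals alongside, and say that they will not always match the Holm decision.

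The cost is a few sentences and the decision on the third primary outcome. No new data or participants are needed. The one real downside is the possible mismatch between the intervals and the Holm decisions.
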